## 5. OBJECTIVES

### 5.1. Hypothesis

A community center for MSM and TGW, with a longstanding experience of early HIV detection, linkage to care and treatment initiation, might be able to create a model with low barrier for Point-of-Care (POC) HCV detection in an understudied population. Through a simple algorithm to achieve detection, confirmation, and treatment initiation at the same day, it would be able to achieve rapid HCV viremia suppression in this scenario. Moreover, this model will be replicable in other European cities, where similar community centers and POC technology are in place.

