### 5.2. Objectives

The primary Goal of this project is to identify HCV acute and chronic infections in HIV-uninfected MSM and TGW community and to offer them a low barrier linkage to care in the context of a fast-track circuit, offering a first visit with a specialist and starting hep C treatment in the same day after confirmation. A total of 10-15 unknown HCV infections are expected to be diagnosed during the study and to be treated. Potential risk factors for increased HCV infection rates include recreational drug use, including "chemsex", PrEP use, sex work, and several sexual behaviors. We will analyze which factors entangle an increased infection risk. This will allow us to focus and intensify screening on people with these factors while reducing the costs of continuous HCV screening in people who maintain at high risk.

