#### Primary objectives

- Determine the prevalence of acute and chronic HCV infection in HIV-uninfected MSM and TGW community. Serologic prevalence will also be determined.
- Establish a fast-track circuit between Sexual Health Community centers and Hospital liver/infection diseases units to offer the possibility of starting treatment quickly after diagnosis and confirmation of HCV viremia on same day.

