## 8. VARIABLES AND MEASURE INSTRUMENTS.

### 8.1. Study Variables

- Determination of acute HCV cases detected by viral load.
- Number of positive viremic results and cases per 100 person-years.
- HCV serologic prevalence.
- Number of positive serologic test with or without positive viremia.
- Time between confirmed diagnostic and start of treatment (Measured in days).
- Number of reinfections at 6 and 12 months after treatment.
- Identification of risk factors using the sexual behavior and demographics questionnaire
- Ratio of satisfaction using "Patient Reported Outcome Measures" (PROMs)
- Causes of treatment delay or loss to follow up
- Reinfections/treatments measured in percentage.

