### 8.2. Endpoints

#### Primary End-points

- Proportion of viremic HCV prevalence in MSM and TGW community in Barcelona at the screening visit.
- Determination of acute cases detected by Viral load during screening visit
- HCV Seroprevalence with non-viremic status at screening visit.
- Number of days between diagnosis and treatment initiation during the study.

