### **11.4. Risks and potential limitations**

As this project will be included in an ongoing project of community screening, recruitment is not expected to be a problem, however intensification of campaigns for promotion of HCV testing will be considered in case of lack of interest in our actual users.

Questions related to risk factors such as number of sexual contacts, drug use, etc. will be asked by the counselor and could produce an underestimation of these risk factors. However, we have been working with this kind of questionnaires for the last 15 years and users have never expressed any problem due to a peer-to-peer service, which allows a safe environment for the clients. All our staff and volunteers are previously selected and adequately trained.

Users with positive results could refuse to attend the medical specialist in the Hospital Germans Trias due to the distance. In this case derivation to other Hospital could be considered. However, treatment will last only 8-12 weeks and usually require no subsequent follow-up. So, in our opinion the interference of this problem in this study would be extremely limited, other Hospitals on the city are working in Test and Treat HCV strategy and referral has been done in the past; also, we will ask for follow up with the participant through telephone calls.

The Partner notification potential Contacts will be performed in our center in collaboration with the Public Health agency to offer testing to positive case contacts. However, in the MSM community this can sometimes be difficult or even not possible because users don't keep in contact with the most part of their sexual partners. From our center we are going to facilitate to get a test in all suspicious cases of contact to other cases.

Our team has been trained during years in the use of rapid tests, including HIV ELISA, PCR, and Syphilis rapid tests. In this cases HCV viral load could be performed at the same time, but also HCV serology could be sent to the lab, as BCN Checkpoint disposes of nurses and doctors at all opening hours (from 8.00 to 20.00 hours) to perform common blood test through standard venipuncture.

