Migrants or undocumented population could have difficulties in their access to the required HCV treatment. In case of confirmation of active HCV and no possibilities of treatment, our center has the possibility to facilitate fast access to the Public Health system to facilitate access to care and treatment, as it is considered a Health priority to eradicate HCV by 2030 in the context of WHO's Global Health Sector Strategy on Viral Hepatitis program. This circuit has been used for HIV confirmed cases and the Public Health Agency is aware of this study and this possibility.

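### The time-to-treatment primary endpoint is defined only for viremic participants who start treatment, so it cannot show how many of all viremic participants the fast-track circuit treats on the same day

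*Combined protocol and SAP*

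**What the plan says.** The second primary objective (section 5.2) is a fast-track circuit "to offer the possibility of starting treatment quickly after diagnosis and confirmation of HCV viremia on same day". The hypothesis (section 5.1) is more ambitious: "Through a simple algorithm to achieve detection, confirmation, and treatment initiation at the same day". Section 5.2 also states: "A total of 10-15 unknown HCV infections are expected to be diagnosed during the study and to be treated".

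Of the four primary endpoints in section 8.2, only one concerns the circuit: "Number of days between diagnosis and treatment initiation during the study". The matching variable in section 8.1 is "Time between confirmed diagnostic and start of treatment (Measured in days". The two clocks are worded differently, one from diagnosis and the other from confirmed diagnosis.

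Section 9 does not name this endpoint. Its general tools are frequencies and percentages, quartiles or standard deviation, and t or Wilcoxon tests. It contains no time-to-event method, no censoring rule and no statement of who is in the denominator.

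Section 11.4 names two reasons why treatment might not start: "Users with positive results could refuse to attend the medical specialist in the Hospital Germans Trias due to the distance" and "Migrants or undocumented population could have difficulties in their access to the required HCV treatment". Of the first it says that "in our opinion the interference of this problem in this study would be extremely limited", without a figure. A secondary endpoint looks at the causes of treatment delay or loss to follow-up.

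**The concern.** A number of days exists only once treatment has started. With no rule for anyone else, the natural summary is a mean or median over starters. That summary leaves out the participants for whom the circuit failed completely, and it can improve when slow or difficult cases are lost rather than treated late.

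The stake is the second primary objective. Section 7.2 (Phase 2) says the final report will focus on how the model could be replicated in other cities. A reader elsewhere needs to know what fraction of viremic people the circuit gets onto treatment and how soon. The written endpoint does not answer that. The 6- and 12-month visits in Tables 1 and 2 apply only to people diagnosed and treated, so a never-starter has no later scheduled visit at which the gap would come to light.

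**Working it through.** The documents give no target, sample size or expected non-start rate for this endpoint, so there is no planned figure to reproduce. What can be checked is the direction of the effect and how it scales.

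**Inputs.** From the documents: 10-15 cases expected (section 5.2). Assumed, because the documents give no value: the never-start share *u* (10%, 20%, 30%) and a same-day share among starters of 80%.

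**Step 1, direction.** For any day *t*:

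share of all viremic started by *t* = (share of starters started by *t*) × (1 − *u*)

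Since 1 − *u* is at most 1, the all-viremic share never exceeds the starters-only share. It is lower as soon as one person does not start and some starters have begun by *t*. With one non-starter the factor is 14/15 = 0.933 for 15 cases and 9/10 = 0.900 for 10 cases, a relative reduction of 6.7% to 10%.

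**Step 2, same-day share and quantiles.** The all-viremic median is the starters' 0.5/(1 − *u*) quantile, and the upper quartile is their 0.75/(1 − *u*) quantile.

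| *u* (assumed) | Same-day share, all viremic | Median = starters' quantile | Upper quartile = starters' quantile |
|---|---|---|---|
| 10% | 0.80 × 0.90 = 72% | 0.5/0.9 = 0.556 | 0.75/0.9 = 0.833 |
| 20% | 0.80 × 0.80 = 64% | 0.5/0.8 = 0.625 | 0.75/0.8 = 0.938 |
| 30% | 0.80 × 0.70 = 56% | 0.5/0.7 = 0.714 | 0.75/0.7 > 1, not reached |

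In all three rows more than half of all viremic participants start on day 0, so the median is 0 days with either denominator. The median in days need not move at all; in these rows the loss shows in the proportion and the upper quantiles.

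**Step 3, a case where the median does move.** Invented times: 15 viremic, 12 starters at 0, 0, 0, 0, 1, 1, 2, 3, 5, 7, 14 and 21 days, 3 never. The starters' median is (1 + 2)/2 = 1.5 days, and 10/12 = 83% start within 7 days. With all 15 in the denominator the median is the 8th value, 3 days, and 10/15 = 67% start within 7 days.

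**Step 4, precision.** Exact (Clopper-Pearson) 95% intervals for the proportion ever starting: 8/10 = 80% (44.4% to 97.5%) and 12/15 = 80% (51.9% to 95.7%). These hold only if 10-15 is the number of viremic cases. Section 5.2 uses that figure for unknown infections, section 11.5 uses it for acute infections, and section 11.5 says the number viremic among the expected seropositives is not known.

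**Step 5, the clock.** Section 6 (Laboratory determinations) equates a confirmed diagnosis with a positive viral load, so for most cases the two clock starts coincide. They can differ for antibody-negative participants with a positive fingerstick viral load, who need a second viral load test (section 7.2, Phase 1). For a same-day claim even one day matters.

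**The case against.** The strongest reply is that the plan is silent rather than wrong. A reader might infer that the protocol excludes never-starters or allows only means and quartiles. It does neither. No section says they are dropped, and section 9 includes frequencies and percentages, so the number treated out of the number viremic could be reported. That stands as a limit on the point. Exclusion follows from the definition of the endpoint and the absence of any rule, not from a stated instruction.

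A reader might also infer that section 11.4 predicts substantial refusal. It says only that users could refuse. It also offers referral to other hospitals, telephone follow-up and a fast route into the public health system, and section 6 provides for asking about treatment received elsewhere. People treated elsewhere can therefore have a valid start date. This also stands, but it does not say how to count those who never start.

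The secondary endpoint on causes of delay or loss makes these people visible. It gives reasons, not the proportion started, and leaves the primary figure unchanged.

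Finally, the objective is worded as offering the possibility of quick treatment, with no target and no test. But the hypothesis speaks of achieving initiation on the same day, and the chosen endpoint counts days to initiation, not days to an offer.

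**Conclusion.** The point holds as a gap in the definition of a primary endpoint. Number of days has no value for a viremic participant who never starts, and nothing in the protocol supplies a denominator, a censoring rule or a proportion started. A starters-only summary can only match or overstate the circuit's performance.

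The size cannot be derived from the documents. The 72%, 64% and 56% figures rest on assumed non-start rates and an assumed 80% same-day share among starters. The documents do not support a claim that the result will be biased by a given amount, or that it must be biased at all. The difference in clock start is a smaller matter, relevant mainly to antibody-negative cases.

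**What to change.** In sections 8.2 and 9:

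- Define the endpoint as the proportion of all confirmed viremic participants who start treatment on the day of confirmed viremia, and by later reporting times that the sponsor chooses in advance. Give exact 95% confidence intervals. Never-starters count as not started.
- Count people treated elsewhere as starters when a start date is obtained.
- Add a cumulative incidence curve of time to treatment start over all confirmed viremic participants, keeping never-starters in the denominator to a fixed data cut-off. Do not simply censor lost cases on the day they are lost; if loss is related to not starting, that removes only part of the bias.
- Report documented spontaneous clearance before treatment separately, for example as a competing event, since the protocol recognises that it occurs.
- Keep days among starters as a descriptive summary.
- Use one clock start in sections 8.1 and 8.2, and say how it applies to antibody-negative cases awaiting a second viral load.
- Record the treatment start date, or its absence at cut-off, for every viremic participant. Tables 1 and 2 have no row for it.

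The cost is wording in two sections and one date field, plus the effort of obtaining start dates for people treated elsewhere through the follow-up already planned. The reported figure may be less favourable.

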#### Secondary End-points

- Characterization of risk factors associated with acute and chronic HCV infection in the MSM and TGW community to inform which individuals will benefit more from HCV screening.
- Evaluation of causes for treatment delay and/or loss to follow up a long the study
- Evaluation of reinfections after treatment during first year post treatment.
- Service user's punctuations achieved after experience in HCV testing.

## 9. STATISTICAL ANALYSIS

A descriptive analysis will be conducted for the following variables: number of subjects, sociodemographic characteristics (gender, age, and partner's HCV status), sexual behavioral patterns (number of partners, drug use while having sex), PrEP use, and biological results. Results are presented in terms of incidence rate ratios (IRRs) and 95% confidence intervals (CIs) and their p-values of active HCV infections and presented as cases per 100 person-years. Depending on the type or distribution of each variable, absolute frequencies (N) and percentages (%), interquartile range (Q1- Q3), or standard deviation (SD) will be calculated. This descriptive analysis will be presented calculated for individuals separately to allow investigation of the association between groups. Categorical variables will be evaluated by Chi square test or Fisher's test, while Student's t-test or Wilcoxon test was used for continuous variables. After the first phase we will conduct a univariate analysis with all independent factors (HCV risk factors). The outcome variable will be the number of new cases of HCV and taking into account the population at risk. Factors associated with HCV infections with univariate p-value<0.1 will be entered in Poisson regression, adjusted by age and gender. A

significant level of 5% will be taken into account for all analysis performed. Descriptive statistics of demographic factors, and sexual behavior patterns and biological results will also be carried out for possible reinfections detected during follow up visits. A descriptive analysis of the patient reported outcomes will also be carried out and presented in the final report. All analyses will be carried out by means of the STATA 14.2 (StataCorp LP, College Station, TX USA).

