### **1.11. Calendar**

- Ethics Committee application: June 2021
- Study starts (first patient in): June 2021
- Recruitment period: 2 years and 2 months.
- Patient follow-up: Single visit. Screening. In case of positive HCV viremia, 6 and 12 months post treatment control will be offered.
- Final report: 2023. Reinfections will be reported during 2024.

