#### **3.6. Expected study duration**

The duration of this study is planned to be 2 years June 2021 to July 2023.

Following see the expected study calendar:

- Ethics Committee application: June 2021
- Study start (first patient in): June 2021
- Recruitment period: 2 years and 2 months
- Patient follow-up: Single visit on Screening. In case of positive HCV viremia, 6 and 12 months post treatment control will be offered.
- Final report: End of 2023. Reinfections will be reported during 2024.

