**Table 1. Study Chronogram Phase 1**

	SCREENING	6 months Post Treatment visit*	12 months Post Treatment visit*
Informed consent	X		
Selection Criteria	X		
SD BIOLINE HCV assay	X		
Cepheid "Xpert® HCV VL Fingerstick"	a X	a X	a X
Xpert® HCV Viral Load	b X		
Routine Serology	c X		
genotype study/Hematology and biochemical analysis	d X		
Sexual behavior & demographics questionnaire	X		
PROMS questionnaire	X	X	X

- a) The participants that obtain a positive result from the SD Bioline HCV assay test will be confirmed with Cepheid "Xpert® HCV VL Fingerstick" to identify HCV viremic cases. Also first 1000 participants with a negative result from the SD Bioline HCV assay test that fulfills criteria mentioned on 1B point, will be confirmed with Cepheid "Xpert® HCV VL Fingerstick" to identify acute HCV infections. \*During V6MPTV and V12MPTM the fingerstick will be offered to all the participants with HCV infection detected during the screening visit.
- b) Acute infections with negative antibodies will be also tested with (Cepheid "Xpert® HCV Viral Load) to confirm viremic cases.
- c) In case of positive serology with negative viral load, standard lab serology will be performed to confirm serology, through standard hospital lab circuit.
- d) For the confirmed HCV Viremic cases, it will be analyzed the following parameters: blood count, Serum Creatinine, AST, ALT, GGT, alkaline phosphatases, direct and indirect Bilirubin, prothrombin time and the genotype study will be performed.

*\* Visits after 6 months and 12 months are optional and only are applicable for those patients that had been diagnosed and treated for HCV infection during the screening visit.*

After one year, a statistical analysis (interim analysis at 6 months\*) of the results will be made to determine associated factors for positive antibody test as well as for positive acute HCV test to set selection criteria for phase 2 of the study. A Draft of HCV pre-test Score will be developed with this first-year analysis and implemented during second phase.

\*Interim analysis will be used to evaluate data collection, correct incidences and to set up data analysis system. This will facilitate the results evaluation at the end of Phase 1 and it will allow to create the pre-test score to start the study Phase 2.

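### Sections 8.1 and 9 put infections found at a single screening visit on a person-years scale with no time at risk defined, and the prevalence of acute infection has no stated denominator

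*Combined protocol and SAP*

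**What the plan says.** **Objective and endpoint.** The first primary objective (Section 5.2) is: "Determine the prevalence of acute and chronic HCV infection in HIV-uninfected MSM and TGW community". The first primary endpoint in Section 8.2 is a viremic proportion at the screening visit. Acute cases detected by viral load are a separate primary endpoint, with no denominator.

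**Scale of analysis.** Section 9 plans incidence rate ratios with 95% confidence intervals and "their p-values of active HCV infections and presented as cases per 100 person-years". For the regression it states: "The outcome variable will be the number of new cases of HCV and taking into account the population at risk". The model is Poisson, adjusted for age and gender, with no offset or exposure term named. Section 8.1 lists "Number of positive viremic results and cases per 100 person-years", and for reinfection "Reinfections/treatments measured in percentage".

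**Follow-up.** Section 1.11 gives "Patient follow-up: Single visit" and Section 3.6 gives "Patient follow-up: Single visit on Screening". The Table 1 footnote says the later visits "are optional and only are applicable for those patients that had been diagnosed and treated for HCV infection"; Table 2 has an equivalent footnote for Phase 2.

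**Who is tested for what.** In Phase 1 (Section 7.2, 1A) all 6,000-7,000 clients are offered the antibody test, and positives go on to viral load. Among antibody-negative clients, viral load is offered to 1,000 who meet risk criteria (1B). In Phase 2 about 300 participants who meet the score criteria have viral load.

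**The concern.** A rate per 100 person-years needs a start and an end of time at risk for each person. Someone seen once, with no recorded earlier negative test, supplies neither. Any rate published under this plan would therefore depend on a time that the analyst supplies afterwards. It would also be on a different scale from the prevalence that the study sets out to estimate. If the model's new cases are read as incident cases, chronic infections found at screening would be mislabelled.

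The second gap concerns acute infection. Dividing acute cases by all clients silently treats untested antibody-negative people as viral-load negative. Dividing by those tested describes a group chosen for high risk, not the community named in the objective. The plan does not say which will be done. Phase 2 aims for a threefold higher prevalence, so the choice of base matters for that comparison too.

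**Working it through.** **1. Reproduce the plan's own figure.** Section 11.5 expects 305 seropositive cases at 4.7%. 0.047 x 6,500 = 305.5, and 305 / 0.047 = 6,489. The implied Phase 1 base is about 6,500, the midpoint of 6,000-7,000. This is a head-count proportion with no time term.

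**2. Look for time at risk.** Sections 1.11 and 3.6 give one visit. The tables confine later visits to treated cases. The reference to a population at risk in Section 9 names neither a population nor a time. The word cohort in Section 7.3 belongs to the sample-size statement. The 1B footnote in Section 7.2 mentions yearly serology for PrEP users, which could supply an earlier negative date for some people, but no section uses it that way. Person-years are therefore not available from the plan.

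**3. Size of the person-time gap.** Rate = 100 x cases / (clients x years per client). Cases: 10-15, the number of unknown infections expected in Section 5.2, applied here to 6,500 clients as an illustration. Both times are assumptions: 1 year is the length of Phase 1; 0.25 year is the 3-month behaviour look-back in 1B, which the plan does not present as time at risk.
- 1 year: 100 x 10/6,500 = 0.15; 100 x 15/6,500 = 0.23.
- 0.25 year (6,500 x 0.25 = 1,625 person-years): 100 x 10/1,625 = 0.62; 100 x 15/1,625 = 0.92.

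The 4-fold change is simply 1/0.25 and holds for any case count.

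**4. What the Poisson ratio estimates.** With one record per person and equal time for all, time cancels from the ratio. What remains is a ratio of proportions at screening, that is, a prevalence ratio. For a binary outcome with prevalence p, the model-based Poisson standard error of a log proportion exceeds the binomial one by 1/sqrt(1-p): 1.005 at 1%, 1.024 at 4.7%, and 1.079 at 14.1% (3 x 4.7%, if the Phase 2 goal is applied to seropositivity). The excess is small to modest, and robust variance removes it.

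**5. Size of the denominator gap.** Section 11.5 expects 10-15 acute cases. Assume that all arise among the 1,000 antibody-negative people tested in Phase 1.
- Tested base: 10/1,000 = 1.0% (exact 95% CI 0.48-1.83); 15/1,000 = 1.5% (0.84-2.46).
- All-client base: 10/6,500 = 0.15%; 15/6,500 = 0.23%.

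The ratio of the two is clients/tested: 6,000/1,000 = 6 to 7,000/1,000 = 7, whatever the case count. If the 10-15 are instead whole-study infections, as Section 5.2 words it, they are 10/10,000 = 0.10% to 15/8,000 = 0.19% of all participants.

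**6. How many antibody-negative clients are untested.** At 4.7% of 6,500, about 6,195 are antibody-negative; (6,195 - 1,000)/6,195 = 84% have no viral-load test in Phase 1.

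**The case against.** The strongest reply is that the primary estimate is already a proportion. Section 8.2 asks for viremic prevalence at screening, Section 8.1 lists serologic prevalence, and Section 9 plans counts and percentages. On that reading the per-person-years figure is one stray secondary quantity. Much of this stands: the primary proportion is not replaced by a rate. But Section 9 attaches its confidence intervals to the incidence rate ratios only, and the rate it promises still cannot be computed.

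Second, new cases may mean newly diagnosed. Known active HCV is an exclusion criterion (Section 7.1), and Section 5.2 speaks of unknown infections. That reading is open, so one cannot infer that the plan will report chronic infection as incidence; the wording leaves it possible.

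Third, Section 8.1 does not tie its person-years line to the screening visit, and reinfections are also found by viral load. However, reinfections have their own lines there, as a number and a percentage. A percentage at fixed 6 and 12 months is an ordinary cumulative proportion and is not an error. Nor is reinfection the only outcome followed beyond screening: days from diagnosis to treatment is a primary endpoint.

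Fourth, on the denominator, 1A and 1B are separate strategies and the acute endpoint can be read as a count. That narrows the point without removing it, because the primary objective asks for a prevalence of acute infection.

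**Conclusion.** The person-time point holds firmly: Sections 8.1 and 9 promise a rate for which the design and plan supply no time at risk, and the scale disagrees with the objective and endpoint. The 4-fold spread in step 3 illustrates how far the rate depends on the assumed time; it does not predict an error of that size.

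The denominator point holds in a narrow form. It concerns antibody-negative acute infection, where the base alone moves the figure 6- to 7-fold. The percentages rest on the assumption that all 10-15 cases fall among the 1,000 tested.

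Two stronger conclusions are not supported. A reader might infer that the risk-factor ratios are invalid; with equal time per person they are sound and need only the right name. A reader might also infer that every prevalence in the study lacks a base. Seroprevalence, and viremia found through a positive antibody test, both rest on everyone given the antibody test. The base of the viremic endpoint becomes unclear only if antibody-negative acute cases are pooled into it, which the plan neither states nor rules out.

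This should be fixed before analysis. It does not undermine the data collected.

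**What to change.** - In Sections 8.1 and 9, replace the person-years, incidence-rate-ratio and new-case wording for screening data with prevalence (n/N, exact or Wilson 95% CI) and prevalence ratios from the planned Poisson model with robust variance.
- Keep person-years only where time at risk is defined: post-treatment reinfection, or repeat testers with a documented earlier negative test.
- Report antibody-negative acute infection by phase, among the antibody-negative people actually tested by viral load, described as a risk-selected (Phase 1) or score-selected (Phase 2) group. Do not count untested antibody-negative people as viral-load negative.
- If acute cases are pooled into viremic prevalence, state the base and say that the figure is a lower bound for all clients.

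Cost: changes of wording and minor analysis work, with the same data and software.
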